This mixed design study (within-subjects Patch factor: active nicotine and placebo patch; between-subjects Product factor: VLNC, e-cigarette, or no alternative product) will allow us to address key questions identified in the RFA-OD-18-002. Specifically, we will assess the potential "impact of novel and/or potential modified risk tobacco products on tobacco behavior" and provide data that estimates the real-world impact of potential regulatory actions. To address these questions, this research will focus on the following aims:

Primary Aim: Examine the ability of VLNCs and e-cigarettes to substitute for smokers' usual cigarettes compared to each other and to no alternative product use in real-world settings (between-subjects effects) and whether these effects are influenced by active nicotine replacement (interaction with within-subject factor).

Secondary Aims: Examine the main effects of VLNCs and e-cigarette use compared to each other and to no product use as well as their interaction with active vs. placebo patch on: 1) the use of study alternative products, and 2) mechanisms underlying product use (e.g.,

"Understanding the real-world impact of the use of three alternate nicotine-delivery products on combustible cigarette use" PI: [name]; UW-CTRI Grant: R01CA239309

withdrawal alleviation, taste, satisfaction). We will also explore the contexts that promote or inhibit switching from conventional cigarettes to alternative products and whether participants' risk perceptions and key person factors (e.g., gender, race, education, psychiatric comorbidity) influence switching, alternative product use, and the potential mechanisms that drive such use behavior.

Recruitment and Study Entry

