
"Understanding the real-world impact of the use of three alternate nicotine-delivery products on combustible cigarette use" PI: [name]; UW-CTRI Grant: R01CA239309

Participants will carry a smartphone to complete EMAs from Orientation through all 4 weeks of product use.

After providing consent at the Orientation visit, study staff will ask if the participant gives the study permission to stay in touch with them and send them reminders about upcoming study contacts during the study via email and/or text message. The staff member will remind them that email and text messaging are generally not a secure way to communicate about their health as there are many ways for unauthorized users to access email and text messages. The staff member will also inform them that they do not have to provide their email address or text message number to participate in this study.

Assessments

To address the primary aim of examining whether VLNCs and e-cigs serve as effective substitutes for conventional cigarettes, and whether use of these alternative products interacts with nicotine replacement, we will conduct extensive assessments of participants' use of their own cigarettes, their use of their assigned alternative products, use contexts, and potential motivators for such use behavior (e.g., withdrawal, reward value of products, risk perceptions). We will also assess person factors and beliefs that may provide insight into who is able and willing to use these alternative products to substitute for cigarettes and which mechanisms might be more relevant for which smokers. To the extent possible we will use measures from the PhenX Toolkit, a collection of broadly validated measures, to enhance the ability to harmonize data from this study with other studies. See Table 1 for the timing of assessments.

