Visit assessments. At each study visit, participants will complete assessments of affect using the well-validated Positive and Negative Affect Scale (PANAS¹²⁷), withdrawal symptoms using the validated Wisconsin Smoking Withdrawal Scale (WSWS¹²⁸), and craving using the Brief Questionnaire of Smoking Urges (QSU-Brief^{129,130}) from the PhenX Toolkit. At Visits 1 through 7 participants will complete the modified Cigarette Evaluation Scale (mCES^{71,131,132}) for cigarettes and at Visits 2 through 7 they will complete the mCES for their assigned alternative product based on their reactions in the last 24 hours. The 12 items of the mCES assess product satisfaction, psychological reward, aversion, enjoyment of respiratory tract sensations, and craving reduction. We will use timeline follow-back methods^{133,134} to assess daily use of participants' own cigarettes, assigned alternative products, and patch if the visit occurs during a Switch Week. These data will be used to supplement EMA reports in case of missing EMA data. Participants will also be asked at all visits except Visit 1 (when they will not have any study products or medication yet) about any possible adverse events from using VLNCs, e-cigs or the patches¹³⁵. At the final visit (Visit 7), we will again assess acceptability, risk perceptions, and

"Understanding the real-world impact of the use of three alternate nicotine-delivery products on combustible cigarette use" PI: [name]; UW-CTRI Grant: R01CA239309

intentions to use cigarettes, VLNCs, e-cigs, and patches. We will also assess how the Juul e-cig compares to other e-cigs participants have used, including what they like or do not like Juul, using a combination of questionnaires and open-ended questions to provide additional information regarding Juul acceptability among adults.

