The secondary outcome is number of VLNCs or JUUL pods used during each switch week. This research will also examine the main effects for Product and Patch and the Product X Patch interaction effect on other exploratory outcomes: 1) the proportion of conventional cigarettes replaced; 2) the use of alternative tobacco products; 3) use contexts; and 4) potential mechanisms such as rewarding value of the alternative products and conventional cigarettes, alleviation of withdrawal symptoms, and taste. We will also explore the impact of person factors (e.g., sex, education, psychiatric comorbidity, dependence) and risk perceptions on the primary, secondary, and exploratory outcomes. We will include these variables as covariates in the analyses, and we will include covariate interaction terms with the between- and within-subjects factors (e.g., sex x Product; sex x Product x Patch) to determine whether these individual difference variables moderate the ability of the alternative products to substitute for conventional cigarettes. To examine use contexts and putative mechanisms driving alternative product use and substitution for conventional cigarettes, we will use the daily EMA data from the evening reports as well as data from the quasi-random daily assessments that will be collected during the Switch Weeks as described above as the exploratory outcome variables. One set of analyses will test summary versions of the outcomes (e.g., means or counts across the Switch Weeks); another set of more fine-grained analyses will preserve the intensive longitudinal data (ILD) aspect of the EMA data collected during each of the 7 days of the Switch Weeks. For the summary versions of the outcomes, the alternative product use outcome will consist of the mean alternative product use events per day reported during the Switch Weeks and the context

"Understanding the real-world impact of the use of three alternate nicotine-delivery products on combustible cigarette use" PI: [name]; UW-CTRI Grant: R01CA239309

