and mechanisms variables will be based on means across the 7 days of the Switch Weeks. For these summary outcomes, we will use statistical models similar to the analyses described above for the primary outcome. For the ILD outcomes, we will create one set of outcomes based on the evening report that assesses experiences across the full day and another set based on the 3 quasi-random comprehensive assessments that occur during the day. For the ILD versions of the outcomes, we will use conditional growth curve models that permit slope and intercept parameters to be evaluated across the 7 days of the Switch Weeks as a function of group; these models also permit examination of other forms of change over time (e.g., linear, quadratic, cubic). We will explore two main approaches to growth curve modeling: a multilevel modeling (MLM) approach¹⁵⁸ and a structural equation modeling (SEM) approach¹⁵⁹. Although similar, each of these modeling approaches has advantages and disadvantages¹⁶⁰ that we will exploit in exploratory analyses. While we are not powered to detect mediation due to funding limitations, we will conduct exploratory mediation analyses to provide information for future research on whether these mechanisms mediate the effects of alternative product use on the use of conventional cigarettes.

Power for Primary Aim Hypotheses

With attrition-adjusted n=54 per group for a between-subjects pairwise comparison, the study is powered to detect a difference of 3.3 cigarettes (SD=6); a corresponding within-subjects pairwise comparison (SD=6, correlation=0.5) is powered to detect a difference of 2.8 cigarettes. Thus, we feel that a total N=225 provides adequate power to detect predicted effects.

Protection of Human Subjects

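### The withdrawal analyses name no pre-product score, although one is already collected; this costs precision in the Product comparisons of exploratory mechanism outcomes

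*Combined protocol and SAP*

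**What the plan says.** The Secondary Aims (opening section of the combined protocol and SAP) include Product effects, and their interaction with Patch, on "mechanisms underlying product use". Withdrawal alleviation is the first example given.

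Under Assessments, the Visit assessments paragraph has participants complete, at each study visit, a measure of affect (PANAS), "withdrawal symptoms using the validated Wisconsin Smoking Withdrawal Scale" (WSWS) and "craving using the Brief Questionnaire of Smoking Urges" (QSU-Brief). Adverse events are asked about at all visits "except Visit 1 (when they will not have any study products or medication yet", so at least one set of scores precedes any product or patch use.

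The Analytic Plan takes context and mechanism outcomes from evening reports and quasi-random smartphone assessments "collected during the Switch Weeks as described above as the exploratory outcome variables". These are analysed in two ways:

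- **Summary outcomes.** The context "and mechanisms variables will be based on means across the 7 days of the Switch Weeks", in models like the primary one, which is a Product by Patch mixed ANOVA with no baseline term.
- **Daily outcomes.** Conditional growth curves (multilevel and SEM) over the 7 days.

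Neither names the WSWS, QSU-Brief or PANAS as outcome or covariate, and neither names a pre-product value of any kind. The Assessments section says "See Table 1 for the timing of assessments", but Table 1 has no row for these three scales.

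**The concern.** Smokers differ persistently in how strongly they rate withdrawal and craving. Product is a between-subjects factor, so those differences enter its error term in full. A score taken before any product is used would remove part of that error at no cost in data. The power section expects only 54 per group after attrition, and the groups are compared pairwise, so a useful Product difference in withdrawal could be missed or estimated more loosely than necessary. Leaving the matter open also leaves the instrument and the baseline to be chosen after the data are seen.

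**Working it through.** **1. The plan's own figure.** The only power statement is for cigarettes: 54 per group, SD 6, detectable between-subjects difference 3.3. Alpha and power are not stated. With two-sided 5% and 80% power assumed, the multiplier is 1.960 + 0.842 = 2.802. The detectable difference is 2.802 × 6 × √(2/54) = 3.23 (3.26 with the t distribution), and power at 3.3 is 81.5% (80.8% with t). The stated 3.3 is reproduced, so the same assumptions are used below.

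**2. Inputs for withdrawal.**
- n = 54 per group (Power for Primary Aim Hypotheses).
- Correlation between the two Switch Weeks, ρ = 0.5. This is borrowed from the within-subjects cigarette statement; none is given for withdrawal.
- Correlation r of the pre-product score with each Switch Week value: not in the documents; 0.3 to 0.7 assumed.
- Unit: the SD of a single week's value.

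**3. Product main effect without a baseline.** It compares groups on the mean of the two weeks, whose variance is (1 + ρ)/2 = 0.75. The standard error is √(0.75 × 2/54) = 0.167, and the detectable difference is 2.802 × 0.167 = 0.47.

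**4. With a baseline covariate.** The share of variance removed is R² = r² / ((1 + ρ)/2). The detectable difference is multiplied by √(1 − R²), and the equivalent group size is 54/(1 − R²).

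| r | R² | √(1 − R²) | Detectable difference | Equivalent n per group |
|---|---|---|---|---|
| none | 0 | 1 | 0.47 | 54 |
| 0.3 | 0.12 | 0.94 | 0.44 | 61 |
| 0.5 | 0.33 | 0.82 | 0.38 | 81 |
| 0.7 | 0.65 | 0.59 | 0.27 | 156 |

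Sensitivity to ρ: at ρ = 0.7 the start is 0.50 and the adjusted values are 0.47, 0.42 and 0.32. For a Product comparison within one Patch condition (one week only), the factor is √(1 − r²), and 0.54 becomes 0.51, 0.47 and 0.38.

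**5. Patch and Product by Patch.** Both rest on the within-person difference between weeks. If the baseline correlates equally with both weeks, its covariance with that difference is r − r = 0, so it explains nothing. A simulation (two groups of 54, 4,000 runs, r = 0.5, ρ = 0.5) gave these standard errors without and with the covariate: Product 0.166 and 0.135; Patch 0.096 and 0.096; interaction 0.195 and 0.195.

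**6. Which score is safely pre-allocation?** Study Visits and Phone Contacts randomizes participants and trains them on the product at Visit 1. Nothing says whether the scales come before or after that step. The retention section pays for 8 study visits, which matches Orientation plus Visits 1 to 7. An Orientation score is therefore implied by the each-visit wording, but not stated. Smartphone data also start at Orientation, but Table 1 puts Orientation on Day 0 and Visit 1 on Day 1, which may leave only about a day of pre-product records.

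**The case against.** Several points on the other side stand.

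- **Not only means.** A reader might infer that withdrawal is analysed solely through 7-day averages. The plan also has growth curves on the daily data. Their intercept lies inside the Switch Week, so they still supply no pre-product value.
- **Not all of the aim.** A reader might infer a loss across the whole second secondary aim. That aim also covers the interaction with Patch, which step 5 shows gains nothing.
- **Not bias.** Randomization makes the Switch Week comparison valid without a starting value. Only precision is at issue.
- **Visit 1 is not automatically a clean baseline.** The remark that "Visit 1 (when they will not have any study products or medication yet" explains why adverse events are not asked about; it does not give the order of questionnaires and allocation. Product assignment is not masked, so a score taken after disclosure could itself be affected.
- **Not excluded.** The covariate list of person factors is given by example and includes dependence and psychiatric comorbidity, which may absorb some of the same variance. Those covariates are there to explore effects and moderation. A baseline rating is unspecified rather than ruled out.
- **Exploratory status.** The Analytic Plan labels mechanism outcomes exploratory. It also favours real-time data for sound reasons, and nothing in the documents shows the visit scales to be the better instrument.

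The correlation may also be low. The baseline is taken during usual smoking and the outcome during requested abstinence, and a visit questionnaire would be adjusting smartphone ratings. None of this removes the point that a collected, relevant score has no stated use.

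**Conclusion.** The point holds as a free gain in precision for the Product comparisons of the exploratory withdrawal and craving outcomes. Under the stated assumptions the detectable difference on the two-week mean falls from about 0.47 to between 0.44 and 0.27 single-week SD. At r = 0.3 the gain is small. The largest figure needs r = 0.7 together with ρ = 0.5, meaning that the baseline tracks each Switch Week better than the weeks track each other, so it is an optimistic end. The documents fix neither correlation and give no SD for withdrawal. They therefore do not support a claim that these comparisons are underpowered, or any single figure for the loss. The missing Table 1 row is clerical, because the text states the timing.

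**What to change.** In the Analytic Plan, prespecify the pre-allocation WSWS score as a covariate for the Product comparisons in the withdrawal models, and the pre-allocation QSU-Brief score in any craving models. In the mixed ANOVA it enters as a between-subjects covariate; in the growth curves, as a person-level predictor. Use the Orientation score if the scales are given there, and say so. Otherwise use the Visit 1 score, with the protocol stating that the scales are completed before allocation is disclosed.

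Optionally, report WSWS and QSU-Brief at Visits 3 and 4 and Visits 6 and 7 as supporting outcomes in all groups. The comprehensive smartphone ratings are triggered by logged product or cigarette use, so someone who logs none contributes none. The visit scales, like the evening reports, do not depend on use. A Table 1 row for the three scales would tidy the schedule.

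The cost is plan wording, possibly one sentence on visit order, and minor added analysis. No new data are required.

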Cigarette and product evaluation	Х	Х	Х		Х	Х		Х	
Carbon Monoxide	Х	Х	Х	Х	Х	Х	Х	Х	
Cotinine		Х	Х	Х	Х	Х	Х	Х	
Ecological momentary assessments	Х	Х	Х	Х	Х	Х	Х	Х	
Adverse health events			Х	Х	Х	Х	Х	Х	

Table 1. Study Assessments

product [if applicable]. The study database will randomize participants, stratified by clinic, gender, and race [White vs. Non-White], to enhance scientific rigor and reproducibility. Participants will use their alternative products as they would like for one week to become comfortable with the product¹¹⁴. Participants will also provide a urine sample for cotinine assessment and be given eight study patches to use during Switch Week 1 when all participants will be asked to abstain from using their own cigarettes for the week. At Visit 2, all participants will complete assessments, provide a breath sample for CO assessment and a urine sample for cotinine assessment, receive feedback on their compliance with the smartphone assessments. All participants will then attend a mid-Switch Week visit (Visit 3) and an end-of-Switch Week visit (Visit 4) to assess biomarkers (a breath sample for CO assessment and a urine sample for cotinine). At Visit 4, the end of Switch Week 1, all participants will be told that they can smoke as usual for a week. In addition, all participants will be given the other type of patch (active or placebo) and asked to use these patches at the start of Switch Week 2 (Visit 5) when they are asked to abstain from smoking their own cigarettes for a week. As during the prior Switch Week, all participants will attend visits mid-week and at the end of the week to assess biomarkers (Visits 6 and 7). To enhance reproducibility, we will attempt to schedule appointments at the same time of day (i.e., within a 2-hour window) for each participant so that there is consistent time for product use prior to providing the biological samples across study visits. We opted to use a 7-day switching period to provide a stronger test of the ability of these alternative products to substitute for cigarettes than in our prior study⁵⁰ (A.5.1), but to minimize the retention problems seen in studies with longer switches¹¹². There are also strong theoretical and empirical reasons to suspect that withdrawal and other motivations for cigarette use will be strongest in the first 7 days of switching, and this design will allow sampling of the full range of work/nonwork environments for most participants¹¹⁵. Participants will complete a follow-up assessment call at 3 months. The baseline visit will last 2 hours, but subsequent visits will last <30 minutes.

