Human Subjects Involvement and Characteristics. A total of 225 participants smokers will be recruited to participate in the proposed research. Specific eligibility requirements are: 1) \geq 21 years old; 2) able to read and write English; 3) no plans to quit smoking in the next 30 days; 4) not currently taking smoking cessation medication; 5) willing and medically able to use nicotine patches; 6) not currently in treatment for psychosis or bipolar disorder; 7) smoking \geq 5 cigarettes per day for the past 6 months; 8) exhaled carbon monoxide (CO) > 5 ppm; 9) no e-cig use within the last month; and 10) not currently pregnant or breastfeeding. Use of other tobacco products (e.g., cigars, chew, *snus*) will not be exclusionary, but we will track such use. Vulnerable populations (e.g., children under 18, prisoners) will not be included in the proposed research.

Sources of Materials. Participants in this study will provide data for the express purpose of research. Data collected from participants in this research will consist of: 1) answers to questionnaires and interviews assessing tobacco use history, demographics, nicotine dependence, affect and psychiatric history, and risk perceptions of cigarettes and alternative products; 2) recording of their own cigarette use and alternative product use and responses to ecological momentary assessment (EMA) prompts on a smartphone; 3) breath samples to permit determination of carbon monoxide, which reflects smoking status; and 4) urine samples to assess biomarkers of exposure to nicotine. All data are retained in the study database. The study database access is limited by physical and password protection to those staff members and investigators directly involved in the study and under the supervision of the UW IRB.

Potential Risks. Risks associated with this research are judged to be minimal. None of the physiological, self-report, or behavioral measures constitute a significant risk. Withdrawal for the Switch Weeks is associated with a number of unpleasant symptoms such as sleep

"Understanding the real-world impact of the use of three alternate nicotine-delivery products on combustible cigarette use" PI: [name]; UW-CTRI Grant: R01CA239309

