To facilitate safety, participants who are not be medically appropriate to use the nicotine patch will not be included in the study (e.g., no previous allergic reactions). Once enrolled, study protocols will assess side effects and unanticipated health events at all study visits and follow-up contacts. We will recommend using a lower dose patch or no patch if the participant experiences symptoms of nicotine toxicity or other troublesome side effects during their Switch Weeks. If participants in the VLNC condition are found to be smoking more than twice their usual cigarettes/day or have an exhaled $CO \ge 100$ ppm, they will be discontinued from the study protocol. We will refer participants their primary care provider as needed. Should excessive risk to study participants be determined, the study will be stopped and all participants notified in a manner appropriate to the nature of the risk.

Confidentiality of participant data and information will be accomplished by using participant ID numbers as unique identifiers, allowing us to keep participant data separate from identifying information. The UW-CTRI Information Technology Administrator, [name], manages the hardware, data, security, and infrastructure below the firewall. Access to the network is limited to only UW-CTRI owned and actively managed devices. All devices automatically lock and are password protected after 15 minutes of inactivity. All portable devices are encrypted for data security and no PHI is stored on local devices. All data stored on the network file server is limited by the principle of least privilege. With respect to the study smartphones, to provide confidentiality and HIPAA compliance, UW-CTRI uses MDM software (mobile device management software) in said study to protect and collect subject data. All

"Understanding the real-world impact of the use of three alternate nicotine-delivery products on combustible cigarette use" PI: [name]; UW-CTRI Grant: R01CA239309

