adverse events (AEs), and individual review of serious adverse events (SAEs) and study participation. In addition, SAEs or AEs that raise concerns (e.g., allergic reaction, significant change in mood or suicidality) will be immediately reported to the study physician who will determine an appropriate course of action, which may include discontinuation of study products. As data become available, the Principal Investigator will review the data on a regularly scheduled basis (initially weekly and later monthly) to determine progress. To facilitate participant safety, study participants must meet study inclusion and exclusion criteria. Once enrolled, study protocols will assess the presence of AEs and SAEs at all study contacts, with the exception of the final assessment call 3 months after the use of study products. Should either excessive risk to study participants be determined, the study will be stopped and all participants notified in a manner appropriate to the nature of the risk and/or lack of benefit. When taking that step the Principal Investigator will consult with the IRB and NCI.

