grant. The NIH grant program director will be notified within five days if the Principal Investigator deems it necessary to suspend this research. In the case of a temporary suspension, the Principal Investigator will develop a plan for continuation of the project and discuss this plan with the NIH grant program director in a reasonable time frame.

Plans for assuring data accuracy and confidentiality and protocol compliance. The Principal Investigator, supported by CTRI analysis staff will develop plans for assuring data accuracy and protocol compliance. Such plans will include data verification and protocol

"Understanding the real-world impact of the use of three alternate nicotine-delivery products on combustible cigarette use" PI: [name]; UW-CTRI Grant: R01CA239309

compliance checks. The Data Manager and IT Manager shall be responsible for ensuring that the data for the project are securely stored, that storage is in compliance with University and federal regulations and that no unauthorized persons have access (electronic or physical) to any participant-identifiable data. All HIPAA regulations and guidelines will be followed, and all study staff must complete approved human subjects and HIPAA training programs.

Data and Safety Monitoring Committee

In addition to the protections outlined in the DSMP (above), this research project will have an independent Data Safety and Monitoring Committee (DSMC). The DSMP specifies overall monitoring that will be conducted by Principal Investigator, including timely reporting of AEs and SAEs. Every six months, the DSMC will convene to review the overall safety data, as well as data on safety summarized by treatment condition. As per NIH guidelines, the objective of these reviews will be to determine whether continued conduct of the research poses any undue risk for participants.

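### The visit adverse-event question is tied to study products and has no pre-product inquiry, in conflict with the safety sections; taken literally, it puts the product versus no-product safety summary at risk of distortion

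*Combined protocol and SAP*

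**What the plan says.** **Assessments, Visit assessments paragraph.** This is the only place that describes what participants are asked. The inquiry is "about any possible adverse events from using VLNCs, e-cigs or the patches". Visit 1 is left out because nothing has been issued by then.

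**Table 1.** The row "Adverse health events" carries six marks, read as Visits 2 to 7. Orientation, Visit 1 and the 3-month call are unmarked.

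**Protection Against Risk.** Here "study protocols will assess side effects and unanticipated health events at all study visits and follow-up contacts". The same section calls for structured or standardized assessment of untoward events.

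**Data and Safety and Monitoring Plan.** Here "study protocols will assess the presence of AEs and SAEs at all study contacts, with the exception of the final assessment call" at 3 months. The reporting paragraph repeats the commitment to structured assessment of untoward events.

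**Data and Safety Monitoring Committee.** Every six months the committee reviews overall safety data "as well as data on safety summarized by treatment condition". No test or threshold is stated.

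**Exposure.** Product is supplied from Visit 1 for four weeks. All arms wear blinded patches, active in one Switch Week and placebo in the other. Switch Week 1 starts at Visit 2 and Switch Week 2 at Visit 5, with a week of usual smoking between Visits 4 and 5.

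**The concern.** The Visit assessments wording asks the participant to link an event to a product before it is reported. The reason given for omitting Visit 1, that nothing has been issued yet, makes sense only if the question is about product effects. The safety sections describe something different: events are collected, and relatedness is considered when deciding what to report.

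The difference matters most for the product versus no-product comparison. Product assignment is open, so participants in the cigarette and e-cigarette arms have something to which they can attribute a symptom throughout. Those in the no-product arm do so only while wearing a patch. Arms with the same true rate of cough, nausea or headache could therefore show different recorded rates.

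The committee sees safety by condition and decides on continuation, and adverse events will be posted publicly. The plan also counts unexpected frequency as one mark of an unanticipated problem, a judgment that a comparable no-product rate would inform. A distorted summary could suggest a product signal that is not there. Events that participants do not link to a product could also be under-recorded, which could hide a real one.

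Separately, cough and shortness of breath are on the lung-injury watch list in Protection Against Risk. Without an inquiry before product use, new symptoms are hard to tell from those already present.

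**Working it through.** The plan states no adverse-event rate, comparison or power, so there is no figure to reproduce. The check sets the sections side by side and then illustrates the possible size.

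**1. Scope and timing**

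| Source | Attributed to a product? | Orientation | Visit 1 | Visits 2–7 | 3-month call |
|---|---|---|---|---|---|
| Visit assessments | Yes | Not excluded by name | Excluded | Yes | Not addressed |
| Table 1 | Not stated | No | No | Yes | No |
| Protection Against Risk | No | Yes, if counted as a visit | Yes | Yes | Yes, as a follow-up contact |
| Data and Safety and Monitoring Plan | No | Yes, if counted as a contact | Yes | Yes | Excluded |

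The sources disagree on attribution, on Visit 1, on Orientation and on the 3-month call.

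**2. What the no-product arm can report if the attributed wording is applied literally**

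- Visit 2 (preceding week: no product, patches not yet due for use): essentially nothing.
- Visits 3, 4, 6 and 7 (patch worn): patch effects only.
- Visit 5 (preceding week: usual smoking, no patch): almost nothing, apart from effects persisting from the earlier patch week.

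So at two of the six scheduled visits, the preceding interval gives this arm almost nothing to attribute an event to.

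**3. Illustration at Visit 2**

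Let b be the background share of participants with an event in the week, equal in all arms, and f the share of those events attributed to the product in a product arm. The no-product arm records zero.

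Apparent excess = b × f − 0 = b × f

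The plan gives neither b nor f; the values below are assumptions. Arm size is 225 / 3 = 75, assuming equal allocation, since the ratio is not stated.

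| b | f | Excess (points) | Expected reports, 75 × b × f | Chance of Fisher p < 0.05 |
|---|---|---|---|---|
| 10% | 25% | 2.5 | 1.9 | 0.01 |
| 10% | 50% | 5 | 3.75 | 0.17 |
| 20% | 50% | 10 | 7.5 | 0.77 |
| 40% | 50% | 20 | 15 | 0.999 |

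The last column is the binomial probability of at least six reports among 75. Six against zero gives a two-sided p of 0.028; five against zero gives 0.058. The plan specifies no such test. The column only indicates how visible the artefact would be.

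**4. Switch Weeks**

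Every arm now wears a patch. With attribution shares f1 in a product arm and f0 in the no-product arm:

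Apparent excess = b × (f1 − f0)

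This is zero if attribution is equal. If the shares differ by 25 points, it is 0.10 × 0.25 = 2.5 points at b = 10% and 0.40 × 0.25 = 10 points at b = 40%.

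**5. If the safety sections govern**

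With events collected regardless of attribution, f drops out and this artefact does not arise.

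**The case against.** The strongest reply is that one clause in the Visit assessments paragraph is a summary rather than a questionnaire script. The instrument is not in the documents, and several safety sections commit to unattributed collection. Events that raise concern go to the study physician with no attribution condition, and any serious event is to be queried. Comparative safety is not a study aim, and the committee's review is descriptive.

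Much of this stands. A reader might infer that adverse events are collected only when blamed on a product and never before product use, so that the by-condition review is biased. The documents do not support that, because Protection Against Risk and the monitoring plan say otherwise. Nor is the no-product arm without any usable reports: it wears a blinded patch in both Switch Weeks. The active versus placebo contrast is within-subject and double-blind with the same question, so it is not affected in this way. A missing baseline does not by itself bias a randomised contrast; it costs precision and makes new symptoms harder to recognise. Visit 1 is not the only pre-product opportunity, since Orientation also precedes product. The affect, withdrawal and craving scales, completed at each visit, partly cover the expected effects of abstinence.

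What the reply does not remove is the conflict. The safety sections promise broader collection but give no question, checklist or form. The one section that describes the question ties it to products, and its reason for omitting Visit 1 fits that reading.

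**Conclusion.** The concern holds in a limited form. The sections conflict on whether events must be attributed to a product and on when they are asked about, and they must be reconciled. If the Visit assessments wording is implemented literally, the product versus no-product safety summary is at risk of distortion, most clearly at Visit 2 and for the week before Visit 5, and to a lesser and uncertain extent in the Switch Weeks.

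The size cannot be computed from the documents. The illustrative excess at Visit 2 runs from 2.5 points (10% background, 25% attributed) to 10 points (20%, 50%), and is larger at higher assumed rates. A reader might infer an excess of 10 to 30 points, but that is a ceiling: it assumes background rates of 10% to 30%, with every event attributed in the product arm and none recorded in the no-product arm. If collection follows the safety sections, this artefact is absent.

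This is a cheap improvement to a stated collection rule. It does not show that the trial's safety data will be wrong.

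**What to change.** In the Visit assessments paragraph and Table 1:

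- Ask all three arms the same question, with no reference to cause: any new or worsened health problem since the last visit.
- Add a fixed checklist of the symptoms the protocol already names under nicotine patches, Potential Risks and Protection Against Risk.
- Ask about current symptoms once before product is issued, at Orientation or Visit 1, and use the full question at Visits 2 to 7.
- Have the study team record relatedness separately, and summarise for the committee by product and patch condition.

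Then align the Visit assessments paragraph, Table 1, Protection Against Risk and the Data and Safety and Monitoring Plan, including whether the 3-month call is covered.

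The cost is a reworded question, one more mark in Table 1 and a few minutes at one visit. The downside is that more non-serious events will be recorded.
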